Protocol Title page

NCT number: NCT03428815

Official Title: Effects of Temperature Control Liner Materials on Long-Term Outcomes of Prosthesis Use

Document Date: January 15, 2020

The protocol has been approved by the responsible Institutional Review Boards. Study subjects are asked by the principle investigators to provide informed consent in accordance with human-subjects protection regulations.

**Subjects:** Subjects are recruited from the community at two sites, in Chester, PA, and Pittsburgh, PA. Inclusion criteria are the use of a prosthesis with liner suspension, at least one year of prosthesis use, a well-fitting socket, the ability to walk with the prosthesis outdoors without notable limitations (K-Level 3), stable weight, and absence of acute medical conditions that would temporarily affect the ability to use prostheses. Exclusion criteria are use of a non-standard liner size, known allergies against liner materials, and any inability to understand the protocol and to comply with the associated tasks, such as maintaining a log of days when the prosthesis could not be used.

Power analysis was based on the cross-over statistical methods above and previous literature and One-sided determination. Halsne, et al. , in an analysis of 12-month step activity data in participants with trans-femoral amputation reported that the average change in step activity scores for subjects in the hot and cold months of the year was significantly higher than in the moderate temperature months of the year corresponding to an effect size of 0.47. This effect size and a sample size of 50 subjects, results in 85% power to detect significant differences.

The assumed effect size would equate a difference in prosthesis utilization of four days per year if the average yearly number of days with prosthesis use has a standard deviation of 10 days. Irrespective of the statistical significance of such an effect, every day of work absence has a relevant economical effect to the employee and the employer. Given the duration of the study and the potential reluctance of subjects to change their liner type, it is anticipated that up to 9

subjects (18%) do not complete the protocol, bringing the statistical power to 80%. Comparable prospective intervention studies in the past have utilized sample sizes between nine and 20.

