A steady state within either of the interventions will be assumed, yet it will be possible to detect any baseline drift or seasonal fluctuations with the proposed repeated measures design. Previous studies have used a repeated measures design to investigate the reliability of outcome measures, such as the Locomotor Capabilities Index and the Two-Minute-Walk test. The Prosthesis Evaluation Questionnaire (PEQ) has been validated in that fashion as well.

Missing values are possible due to drop-out and intermittent non-compliance with the data collection schedule. This would not invalidate “year-on-year” comparison of the remaining data sets. Provided that baseline characteristics can be sufficiently described by existing data, it may also be possible to interpolate and extrapolate missing data points with some accuracy.

Despite the long duration of the data collection, the intervention itself will have a comparably low burden on the subjects’ daily lives, which is expected to make participation appealing to a wide range of potential subjects who are targeted by online and offline postings.

**Methods:** The protocol utilizes a double-blind longitudinal cross-over research design. A sample of trans-tibial prosthesis users is randomly assigned to one of two groups. While subjects in one group receive PCM liners, the members of the other group are fitted with regular gel or silicone liners. After six months, the first group receives conventional liners (and turn their PCM liners in) and the second group receives PCM liners (Table 1). Prostheses in either group are equipped with activity monitors, and participants are asked to keep daily notes of any perceived issues with their residual limb or socket fit. In regular intervals, subjects’ physical performance capabilities and prosthesis-related quality of life, including limb and overall health, is assessed using standardized methods.

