Upon entering the study, every subject receives two identical new liners that match their currently used one in size as measured by a credentialed prosthetist. The liner material is either the same as in their existing liner or PCM infused silicon, depending on group allocation. In order to blind the subjects and study personnel to the treatment, all study liners are custom ordered for each subject from the same manufacturer (Willowood, Sterling, OH) in a uniform color and outer fabric design. The packaging is uniform as well apart from a label containing the study participant number provided at ordering. Every liner is imprinted with a unique serial number that is the only sign by which it can be identified as a PCM or conventional liner. The manufacturer provides a list of these numbers, which will only be accessed by research personnel

once the data collection and analysis procedures are completed, so that the results can be attributed to the proper group. Two identical liners are provided to allow subjects to alternate between them on a daily basis, which is recommended practice in order to allow cleaning and air drying liners and to maximize life time of the material. (A regular life time of six months continuous wear is common for prosthesis liners.) Subjects are instructed to handle and rotate the liners in their usual way, in order to assure realistic test conditions, but are asked to not wear their previously existing liner for the duration of the study.

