Subjects are asked to continue their regular activities of daily life while wearing the new liner, and to make a note of any days during which the prosthesis could not be used due to residual limb health issues, as a redundancy to the step counter data. About every two weeks, a member of the research team will schedule a 5-minute appointment with the subject to read out Stepwatch data. Subjects are not required to come to the research site for the respective appointments, which may be scheduled at their homes or places of work according to subjects’ preferences. While the Stepwatch monitor can store up to 50 days of data, two-week-intervals have been chosen to mitigate the adverse effects of possible equipment malfunction or application errors. Any adverse events or other unsolicited reports will be recorded as they occur.

Every six weeks, appointments are scheduled to conduct the 2MWT, complete sections “About the prosthesis”, “Specific Bodily Sensations”, “Ability to Move Around”, “Satisfaction with particular Situations”, and “Importance of different aspects” of the PEQ, and read out step data.

At the 6-month appointment, after completing 2MWT and PEQ, subjects turn in their two study liners and receive two new liners, representing the respectively other variety. Following a short rest, subjects will complete the 2MWT and PEQ once more before the test day is concluded while wearing the new liner.

The 12-month appointment marks the end of the data collection for this study. Individuals blinded to liner type will perform all data collection.

Subjects receive a compensation of \$30 per site visit for a total compensation of \$270. This payment schedule is intended to reduce the occurrence of drop-outs.

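### For users of non-silicone liners the base material is a second possible sign of liner type, so the double-blind claim is not supported for them

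*Combined protocol and SAP*

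**What the plan says.** The Methods section opens its design description with: "The protocol utilizes a double-blind longitudinal cross-over research design". It describes the control condition by saying that "the members of the other group are fitted with regular gel or silicone liners", so gel and silicone are named as two kinds of conventional liner.

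The study-liner paragraph, which follows Table 1 in the Methods, sets the material rule: "The liner material is either the same as in their existing liner or PCM infused silicon, depending on group allocation". (I read silicon there as silicone.) To blind subjects and staff, liners are ordered from one manufacturer "in a uniform color and outer fabric design". On packaging it says: "The packaging is uniform as well apart from a label containing the study participant number". It then describes the serial number as "the only sign by which it can be identified as a PCM or conventional liner".

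Eligibility does not depend on liner material. Under Subjects, "Inclusion criteria are the use of a prosthesis with liner suspension", with further criteria on experience, fit, mobility and health, none of which excludes gel users. At the 6-month visit subjects hand in their liners and "receive two new liners, representing the respectively other variety". They complete the walk test and the PEQ before the swap and again afterwards on the same day.

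**The concern.** The masking measures deal with what the liner looks like from outside and how it is packed. They say nothing about the material worn against the skin. For a silicone user this need not matter, since both study liners are silicone. For a gel user the two liners differ in base material, in a way that lines up exactly with control versus PCM.

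These subjects have at least a year of prosthesis use, handle and alternate the liners themselves, and wear each type for six months. If they can tell the materials apart and work out which one carries the PCM, their ratings can reflect what they expect of it. Four of the six secondary outcomes are PEQ self-ratings. A favourable PEQ result would then be reported as double-blind evidence although an unknown part of the sample may not have been masked. The plan has no analysis by liner material that would let a reader judge this.

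**Working it through.** **Step 1: apply the material rule to each type of user.** The inputs are the control definition and the material rule, both in Methods.

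| Existing liner | Control period | PCM period | Base material differs? |
|---|---|---|---|
| Silicone | silicone | PCM in silicone | no |
| Gel | gel | PCM in silicone | yes |

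**Step 2: compare with what is made uniform.** Colour, outer fabric and packaging are uniform. Base material is not mentioned. In the second row it therefore remains as a possible sign of liner type in addition to the serial number, and the statement that the serial number is the only sign does not follow.

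**Step 3: go through the outcomes (Outcome Variables).**

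- The four PEQ ratings (function, well-being, mobility, satisfaction) are self-rated and directly exposed.
- The two-minute walk depends on effort and is less exposed.
- Days of prosthesis use combine the subject's log with step data, and the information is used only where both agree. A biased log cannot by itself create an agreed non-use day.
- Step count is measured by device.

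**Step 4: illustrate the size.** The plan states no figure on this point, so there is none to reproduce. The documents give n = 50 (Subjects). Everything else here is assumed: a share *g* of gel users, a shift *b* in favour of PCM among them (in SDs of the paired difference), no true effect, and a paired *t*-test at 5%. The change in variance from mixing shifted and unshifted subjects is ignored.

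- Pooled shift: *s* = *g* × *b*.
- Noncentrality: *s* × √50 = *s* × 7.071.
- False-positive rate: the probability that a noncentral *t* with 49 df exceeds 1.677 (one-sided), or lies beyond ±2.010 (two-sided).

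| *g* | *b* | *s* | Noncentrality | One-sided | Two-sided |
|---|---|---|---|---|---|
| 10% | 0.1 | 0.01 | 0.071 | 5.8% | 5.1% |
| 25% | 0.2 | 0.05 | 0.354 | 9.7% | 6.4% |
| 50% | 0.2 | 0.10 | 0.707 | 17.2% | 10.7% |

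Both columns are shown because the plan mentions a one-sided approach only for the power analysis. The Statistical Plan does not state sidedness for the tests. The planned mixed models and Benjamini-Hochberg adjustment are not represented in these figures.

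**The case against.** The strongest reply is that noticing is not identifying. No sentence says that a wearer or assessor can see or feel the difference between gel and silicone in these liners, and they are custom ordered precisely to blind people. Every subject also receives new liners of uniform appearance, so even the control may differ from the old one. To name the PCM liner, a gel user would have to know that the control copies their own material and that PCM comes in silicone. What subjects are told cannot be seen, because the consent text is not part of the document. This stands. A reader might infer that blinding is broken for gel users; the documents support only that it is not secured and may fail.

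Three other strong readings also go too far:

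- **That the gel share could never be known.** The control must match the existing material and each liner is ordered individually, so the share should be recoverable from the orders. What is missing is a planned use of it.
- **That the main outcome is seriously biased.** The agreement rule limits what the log can do, and step count is device-measured. Activity could respond to expectation, but the documents offer no evidence that it does.
- **That the effect in same-material subjects is a clean masked estimate.** This is unproven, since PCM might be recognised in other ways. In gel users the contrast also contains any real effect of moving between gel and silicone.

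None of this rescues the wording on the serial number, which has no support for gel users as the plan is written.

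**Conclusion.** The point holds as a gap between the masking claim and the material rule, confined to users of gel or other non-silicone liners. For them the double-blind and sole-identifier statements are unsupported. Whether masking actually fails rests on two inferences: that the materials are perceptibly different, and that subjects can link the difference to PCM.

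The consequence falls mainly on the four PEQ ratings. Its size cannot be determined from the documents. The illustrated range, about 6% to 17% one-sided or 5% to 11% two-sided against a nominal 5%, depends wholly on the assumed share, shift and direction. It should not be read as an estimate for this trial. If few subjects use gel, the effect is negligible. The change is still worth making, because it costs little and affects how the PEQ results may be described.

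**What to change.** 1. In both Methods paragraphs that make the claim, state how base material is matched or masked between a subject's two study liners. If it is not, limit the double-blind and serial-number statements to subjects whose two liners share a base material.
2. Carry each subject's existing liner material into the analysis dataset. It is already needed to order the control.
3. In the Statistical Plan, for each of the four PEQ ratings, report the liner effect in same-base-material subjects beside the pooled estimate. Note that a gap between the two may reflect a real material effect as well as expectation.
4. Optional: at the 6-month visit before the swap, and at 12 months, ask which liner the subject believes they wore. Answers will partly reflect perceived benefit.

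The cost is wording, one data field and one additional estimate per PEQ rating. Treatment, randomisation and sample size do not change. The drawback is lower precision in the subset: if half of 50 subjects qualified and the SD were the same, the standard error would be √(50/25) = 1.41 times as large.

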***Outcome Variables:*** The main outcome variable is prosthesis utilization and is operationally defined as “total step count per time” and as the “number of days with prosthesis use per time”. Prosthesis utilization is the clinically most relevant variable, as it describes the extent to which a person’s limb loss affects their social and economic participation. To determine the number of days of prosthesis use, self-reported information will be evaluated along with step count data. A day without substantial prosthesis use will be assumed if the daily step count is below the 20th percentile for the average daily step count of the respective individual over the full year. Only if both methods agree on the number of dates without prosthesis will the information be used for analysis in order to reduce the errors caused by inaccurate memory or by malfunctioning equipment.

Secondary outcome variables will be “Step count bouts per time unit”, “Two-minute walk distance”, “Prosthesis function rating”, “Well-being rating”, “Mobility rating”, and “Satisfaction rating”, the latter four of which are based on question groups 1, 2, 4, and 5 of the PEQ respectively. Analyzing those variables will allow a more comprehensive understanding of the effects of PCM liners and may inform the hypotheses of subsequent studies investigating their function mechanisms.

Depending on the eventual sample composition, it may be possible to extract incidental findings on the effects of demographic and anthropometric factors on measured outcomes with the

different liners. Any such results may be useful as pilot data for subsequent studies to further investigate the utility of PCM in prosthetics.

Several possible comparison variables are deliberately not included in this clinical trial.

Monitoring changes in liner temperature or material properties during use would necessitate the use of additional data collection equipment, which would be likely to interfere with the regular use of the liners and thus pose a bias to the measured data. Also, it is unclear how temperature data should be interpreted (e.g., whether lower temperatures are always better than higher, or steady temperatures better than fluctuating) to become clinically meaningful. It is anticipated that the findings of the present study motivate subsequent research to investigate the function mechanisms of PCM liners and to better explain the results of this study.

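### The subject log covers only limb-health non-use days, yet must match a step-count measure that ignores cause; the resulting loss of days-of-use data depends on a discard unit the plan does not state

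*Combined protocol and SAP*

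**What the plan says.** One of the two operational definitions of the main outcome is the "number of days with prosthesis use per time" (Outcome Variables). For it, "self-reported information will be evaluated along with step count data".

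- **Log.** The instruction to subjects, in the Methods text after Table 1, is to note "any days during which the prosthesis could not be used due to residual limb health issues, as a redundancy to the step counter data".
- **Step rule.** Under Outcome Variables, "A day without substantial prosthesis use will be assumed if the daily step count is below the" person's own 20th-percentile value for the year. Cause plays no part.
- **Agreement rule.** "Only if both methods agree on the number of dates without prosthesis will the information be used for analysis". The stated purpose is to limit errors from faulty recall and faulty devices. The plan does not say whether disagreement removes a date, a read-out interval, a half-year or a subject, or how a disagreement is resolved.

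The log is described differently in two other places. The exclusion criteria under Subjects speak of "maintaining a log of days when the prosthesis could not be used", with no cause given. The opening of Methods says subjects "keep daily notes of any perceived issues with their residual limb or socket fit", which adds socket fit and concerns problems rather than days of non-use.

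**The concern.** A redundant measure has to capture the same thing as the measure it backs up. Here the log is limited by cause and the step data are not. If a subject leaves the prosthesis off because of influenza or a repair, the monitor shows a non-use day and the log, kept exactly as instructed, shows none. The same holds for heat or comfort, if the subject does not regard these as limb-health problems. The counts differ although neither memory nor equipment failed, which is all the rule was meant to guard against.

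Two things are at stake. First, if disagreement removes whole intervals, the intervals kept are those without other-cause days off. Missingness then depends on the outcome itself. Second, if a date counts as non-use only when both sources show it, nothing is discarded, but the outcome becomes limb-health non-use without the plan saying so. In either case, days off for heat or comfort, which a temperature-control liner might plausibly change, may not contribute to the comparison.

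**Working it through.** **Inputs from the plan.** The log's scope, the two-week read-outs and the six-month periods come from Methods. The step rule and the agreement rule come from Outcome Variables. The plan gives no expected agreement and no rate of other-cause non-use, so there is no figure to reproduce.

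**Assumptions.** Other-cause non-use days are Poisson with mean m per subject-year; m = 1, 2 and 4 are illustrative. The log is kept exactly as instructed, the monitor is faultless, and non-use means zero steps. The last assumption isolates the log problem from the step threshold.

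**Step 1: when the counts agree.** In an interval let L be the limb-health non-use days and X the other-cause non-use days. The log gives L and the monitor gives L + X. They agree only if X = 0.

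**Step 2: usable share by unit.** P(X = 0) = exp(−m × t), with t the interval length in years.

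| Unit judged | t | m = 1 | m = 2 | m = 4 |
|---|---|---|---|---|
| Year | 1 | exp(−1) = 37% | exp(−2) = 14% | exp(−4) = 2% |
| Half-year | 1/2 | exp(−0.5) = 61% | exp(−1) = 37% | exp(−2) = 14% |
| Two-week read-out | 1/26 | exp(−0.038) = 96% | exp(−0.077) = 93% | exp(−0.154) = 86% |

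**Step 3: single dates dropped.** The expected share of days lost is m/365: 1/365 = 0.3%, 2/365 = 0.5%, 4/365 = 1.1%.

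**Step 4: non-use counted only when both sources show it.** No data are lost. The non-use count is L, and the X days are treated as days of use.

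**Step 5: the step cut as written.** Read as a percentile of a person's own daily counts, it flags about 0.20 × 365 = 73 days a year, or 0.20 × 182.5 = 36.5 per half-year if evenly spread. The counts would then match only if the subject logged about 73 limb-health days. For most subjects the bulk of these flagged days would presumably be worn, low-activity days, which even a perfect all-cause log leaves blank. Correcting the log alone therefore does not make the sources agree.

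**The case against.** The strongest reply is that the harm is indeterminate and may be small. The discard unit is unstated, m is assumed, and the same assumptions leave anything from 2% to 96% of units usable. This stands. A reader might infer from the yearly figures that the trial would keep only about 18, 7 or 1 of 50 subjects (50 × 0.368, 0.135, 0.018). The documents do not support that, because nowhere do they say that agreement is judged per subject-year.

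Second, the percentile cut may already produce disagreement for nearly everyone, so the log wording adds little under the plan as written. That is fair as to size. But the log problem survives repair of the cut: the working through Step 4 already takes non-use as zero steps.

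Third, the daily notes in Methods partly cover socket fit, and heat or sweat at the limb might be noted as a limb issue. This narrows the gap for those days. It does nothing for illness or repair, and those notes do not ask for days of non-use.

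Fourth, other-cause days unrelated to the liner should fall similarly in both periods of a within-subject crossover, and the planned mixed models keep subjects with partial data. This limits bias from unrelated causes, leaving mainly a loss of precision. It is less reassuring for heat or comfort days, which may differ by liner, and for intervals removed because of the very outcome they contain.

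Two further inferences go too far. The log is not useless against monitor failure: a limb-health day off has a log entry, and the two-week read-outs are there partly to limit the effect of malfunction. Only on an other-cause day off do a blank log and zero steps look the same as a dead monitor. Nor does the Subjects wording already define all-cause non-wear: a prosthesis that could not be used is not the same as one that was not worn.

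**Conclusion.** The mismatch is real and rests on the plan's own wording: a cause-restricted log is required to agree in number with a cause-blind step measure. A correctly logged and correctly measured day off for another reason creates disagreement. Chance offsets, such as a logged day with steps above the cut, could hide it but would not validate the count. The three descriptions of the log must also be reconciled.

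The size cannot be determined from the documents. It runs from about 1% of days or less to nearly all subject-years, according to the discard unit and the assumed m, with a perfect log, a perfect monitor and a zero-step definition of non-use. If both sources must show a date, no data are lost but the outcome changes meaning.

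The effect is confined to the days-of-use definition; total step count is unaffected, so it would be wrong to conclude that the main outcome as a whole is compromised. Severity: should-fix, handled together with the step threshold and the agreement rule.

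**What to change.** Make these changes together:

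1. Reword the log instruction in Methods so that subjects record every day the prosthesis was not worn, with a tick-box reason: limb or skin; socket fit, heat or comfort; other illness; repair; choice. Align the descriptions under Subjects and at the start of Methods.
2. Replace agreement on the number of dates with a date-by-date comparison of log and step data at the existing two-week read-outs, while recall is fresh. Count non-use when both sources show it for that date, and set only unresolved dates to missing.
3. Replace the 20th-percentile cut with a step criterion that identifies non-wear, for example zero or near-zero steps. Without this, the sources will still disagree on many worn, low-activity days, and the missing-date rule in item 2 could remove up to about a fifth of days.
4. State that the days-of-use outcome is based on all-cause non-use, and report limb-, fit- or comfort-related non-use as supportive. This is a choice of what to estimate. It suits the stated rationale of social and economic participation, but it goes beyond the current log wording and should be declared.

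The cost is one reworded instruction with tick boxes, a revised outcome definition, slightly more burden on subjects, and a minute or two at each read-out. Unlogged days and their reasons cannot be reliably recovered at analysis, so the log change has to be made prospectively.

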Skin health, although an important outcome of prosthesis use, has likewise not been included in the study protocol. Assessment of residual limb skin health may help detect a number of adverse reactions to prosthesis use, ranging from skin abrasion to tissue necrosis. Measuring skin health outcomes results is fairly subjective and requires timely notification and assessment as skin issues occur. It is thus challenging to apply a reliable measure consistently across time, and especially across different research sites. This study focuses on prosthesis utilization, and considers skin and other health issue to have effects on the measured quality and quantity of prosthesis utilization. For the purposes of this research, the mechanisms that may lead to changes in that outcome variable are not the focus, and investigating them is therefore deferred to subsequent studies.

***Statistical Plan and Data Analysis:*** Exploratory data analysis will be conducted prior to formal statistical analysis. The distributions of all key variables will be examined to check for data errors and ensure that modeling assumptions are not violated. Numerical summaries including

means, standard deviations, medians and histogram graphical techniques will be used for continuous variables and frequencies will be computed for categorical variables.

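### Adverse events are collected passively with no planned summary by liner, and notes of limb problems on days of continued wear enter no analysis, so such problems could show only indirectly

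*Combined protocol and SAP*

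**What the plan says.** - **Adverse events.** In the Methods section, the paragraph on Stepwatch readouts ends: "Any adverse events or other unsolicited reports will be recorded as they occur". The wording places adverse events among reports that nobody asks for. The document sets no standard adverse event question and no event definition.
- **Notes, first description.** Early in Methods, "participants are asked to keep daily notes of any perceived issues with their residual limb or socket fit".
- **Notes, second description.** Later in Methods, subjects are to "make a note of any days during which the prosthesis could not be used due to residual limb health issues", as a back-up to the step counter.
- **Use of the notes.** Under Outcome Variables, for the number of days with prosthesis use, "self-reported information will be evaluated along with step count data". A condition follows: "Only if both methods agree on the number of dates without prosthesis will the information be used for analysis".
- **Symptoms that are asked about.** "Every six weeks, appointments are scheduled to conduct the 2MWT, complete sections “About the prosthesis”, “Specific Bodily Sensations" and three further PEQ sections. Group 2 (bodily sensations) is analysed as the secondary Well-being rating.
- **Skin health.** The end of Outcome Variables names reactions to prosthesis use "ranging from skin abrasion to tissue necrosis". It leaves skin health out as an outcome because measuring it is fairly subjective, "requires timely notification and assessment as skin issues occur", and is hard to do consistently over time and between sites. Skin problems are expected to act through the quality and quantity of utilization.
- **Analysis.** The Statistical Plan and Data Analysis section covers the outcome measures, baseline comparisons and missing data. It has no adverse event table and no comparison of limb problems by liner.

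**The concern.** The trial compares two liner materials worn against the residual limb for six months each, and its own text lists skin reactions that can be serious. It relies on such problems showing through utilization. That works when a problem stops or reduces walking. It works less well when a subject has an abrasion or a poor fit and keeps walking, because steps and days of use may then change little. If the phase change material (PCM) liner did as well or better on utilization, a reader would next ask whether limb problems were more or less frequent on it. The plan collects raw material for an answer in the daily notes, but gives it no route into the results. The two descriptions of the notes also differ, so subjects or sites could keep different records.

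**Working it through.** The documents state no figure on this point, so the check traces each data source to the outcome list and the analysis.

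| Source | How obtained | Stated use | Counts limb problems during wear? |
|---|---|---|---|
| Adverse events | Unsolicited, as they occur | None stated | Only if volunteered; no table by liner |
| Notes of non-use days | Kept by subject | One definition of the main outcome, subject to the agreement rule | No, non-use days only |
| Notes of any limb or socket issue | Kept daily by subject | None stated for days of continued wear | Holds the information, but unused |
| PEQ group 2 | Asked every six weeks | Well-being rating (secondary) | No, a 0 to 100 rating |
| Two-minute walk | Every six weeks | Secondary outcome | No |
| Step counts and bouts | Continuous | Main and secondary outcomes | No |

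**Outcome count.** The main outcome has two definitions and there are six secondary variables: 2 + 6 = 8 measures. None is a count of limb problems on days of wear.

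**Three kinds of day with a limb problem.**
1. Prosthesis not worn. The day is noted and the step count is low, so it can enter the days-of-use outcome if the two methods agree.
2. Prosthesis worn, few steps. Total steps fall. The day may drop below the individual's 20th-percentile threshold without being noted as a non-use day. It then appears as a mismatch between the methods, not as a limb problem.
3. Prosthesis worn, usual steps. Neither definition of the main outcome changes. The problem may affect the next PEQ rating or walk test. Otherwise it stays in the notes.

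**Contacts already planned, per subject.** Readouts about every two weeks give 52 / 2 = 26 a year. Compensation of $270 at $30 per visit implies 270 / 30 = 9 site visits, one of them the first appointment, so 8 follow. These carry the 10 time points in the statistical plan, because the 6-month visit is measured on both liners. If each six-weekly visit also serves as the readout then due (an assumption, though step data are read out there), 26 - 8 = 18 contacts are readouts only. The 8 visits ask about bodily sensations through the PEQ. The 18 readouts are described only as reading out the monitor, and the document has nobody review the notes at them.

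**Scope of the reasons for leaving skin out.** Subjectivity and consistency over time and sites are reasons against a scored skin outcome. They do not bear on listing reported problems by liner period, which needs no skin score.

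**The case against.** The case on the other side is substantial. The exclusion of skin health is explicit and reasoned. The requirement for timely notification is stated for measuring skin health, not as a safety rule that the plan then breaks. The main outcome does draw on self-report of limb-related non-use days. PEQ group 2 is asked every six weeks and analysed, and Methods says that the quality-of-life assessment includes limb health. A liner that persistently caused discomfort could therefore show in that rating, in walk distance, or in step totals and bouts, which can fall without a whole day lost. The readout is a 5-minute appointment, so an added question is a noticeable share of it.

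Most of this stands, and it rules out three readings that a reader might infer. The first is that the notes feed no outcome analysis; the non-use-day notes do. The second is that limb problems during wear would go unseen; they could show indirectly. The third is that no contact asks about the limb; the six-weekly visits do so through the PEQ. A reader might also infer that a worsening lesion would go unattended. That would be an inference from silence: adverse events are to be recorded, and the removed consent pages may tell subjects how to report problems.

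None of this supplies an event count. A rating has no onset date, no number of episodes and no number of subjects affected. The reasons against a skin outcome also do not explain why the adverse events that are recorded are not tabulated by liner.

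**Conclusion.** The point holds in limited form. Adverse event capture is passive, no summary by liner is planned, and notes of limb or socket problems on days of continued wear have no stated use. The trial could not report how often such problems occurred on each liner. This is a gap in safety reporting that is cheap to close. It does not undermine the utilization comparison.

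No numerical size is attached. The documents give no rate of limb problems and no rate at which unsolicited reporting picks them up. An upper limit for the proportion affected if none were recorded would need an assumed capture rate, and would bound a single proportion, not a difference between liners.

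The conclusion rests on two readings: that adverse events are grouped with unsolicited reports, and that silence in the statistical plan means no summary is planned. How far PEQ group 2 covers skin problems cannot be settled, because the documents do not list its items.

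**What to change.** 1. **Methods, notes.** Reconcile the two descriptions, any perceived issue or non-use days only, and state one scope for all subjects.
2. **Methods, visits.** At the existing six-weekly visits, and at the two-weekly readouts where feasible, blinded staff read the notes and ask one standard open question about the limb and socket. Each problem is recorded with onset date, end date and study period, not liner type, so that the blind is kept. Problems are passed to the site investigator, who decides on any action.
3. **Statistical Plan and Data Analysis.** Add a descriptive table of adverse and limb events, and of subjects affected, by liner period. Liner type is attributed when the manufacturer's serial-number list is opened, as for the other results. No skin score and no hypothesis test are needed.

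**Cost.** One question, one form and one table, with no new visits. At the six-weekly visits alone this is up to 8 x 50 = 400 contacts; with every readout included it is about 26 x 50 = 1,300. Each added minute across all 1,300 is 1,300 / 60, or about 22 staff hours over the trial. More minor events will be recorded, and the 5-minute readouts will run longer where the question is asked.
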